### 7.4 Post-Chemotherapy Assessment

The participant will complete a post-chemotherapy assessment approximately 4 weeks after the end of chemotherapy (range: 2 to 12 weeks post-chemotherapy). The CRA will meet with the participant to complete a cognitive assessment for visual working memory (DMS), verbal learning and memory (HVLT-R), processing speed (RVP), executive function (OTS), attention and working memory (Digit Span), verbal fluency (COWA), and semantic fluency (ANT). The participant will also complete self-report assessments for cognitive function (PROMIS-Modified Cognitive Function), cognitive effort (NASA-TLX), depression (PROMIS-D), anxiety (PROMIS-Anxiety), sleep disturbance (PROMIS-Sleep Disturbance), fatigue (FACT-F), functional status (KPS), hormonal status, HRQOL (FACT-G), and beliefs about the necessity and concerns of taking memantine (Modified BMQ-Specific). See Appendices A – Q. In participants who were not classified as post-menopausal at study entry, FSH levels will be drawn. The participants will also be asked if they engaged in any other activities or received medications during the study period that they believe preserved their cognitive function. When assessments cannot be completed, this will be noted in the eCRF. Following completion of all post-chemotherapy assessments, participants will be compensated for their time with a gift card. Participants must complete all aspects of the study visit in order to receive the compensation. As with the pre-chemotherapy assessment, the post-chemotherapy assessment will be conducted in private rooms at UNC Breast, Hillsborough Oncology, and UNC REX Cancer Center clinics; in private rooms at participants' homes; over the phone; and by video conferencing after confirming that subjects are in a private location. The post-chemotherapy assessment and questionnaires will be offered by email and mail as is necessary and feasible.

### 7.5 6-Month Post-Chemotherapy Assessment (subset only)

Participants who at the time of initial consent indicate interest in being observed over extended longitudinal follow-up will complete an additional assessment 6 months after completing chemotherapy (range: 4 to 8 months post-chemotherapy). The CRA will meet with the participant to complete a cognitive assessment for

visual working memory (DMS), verbal learning and memory (HVLT-R), processing speed (RVP), executive function (OTS), attention and working memory (Digit Span), verbal fluency (COWA), and semantic fluency (ANT). The participant will also complete self-report assessments for cognitive function (PROMIS-Modified Cognitive Function), cognitive effort (NASA-TLX), depression (PROMIS-D), anxiety (PROMIS-Anxiety), sleep disturbance (PROMIS-Sleep Disturbance), fatigue (FACT-F), functional status (KPS), hormonal status, and HRQOL (FACT-G). See Appendices A – P. Following completion of all post-chemotherapy assessments, participants will be compensated for their time with a gift card. Participants must complete all aspects of this study visit in order to receive the compensation. As with the pre-and post-chemotherapy assessments, this will be conducted in private rooms at UNC Breast, Hillsborough Oncology, and UNC REX Cancer Center clinics; in private rooms at participants' homes; over the phone; and by video conferencing after confirming that subjects are in a private location. The post-chemotherapy assessment and questionnaires will be offered by email and mail as is necessary and feasible.

#### **7.6 Concurrent CNS Active Medications**

All concurrent CNS active medications, including psychostimulants, acetylcholinesterase inhibitors, other NMDA receptor antagonists, antidepressants, anxiolytics, antipsychotics, antiepileptics, and antihistamines will be documented at Baseline/Screening and throughout the study as summarized in the Time and Events Table in Section 7.1.

#### **7.7 Demographics**

Demographic information (date of birth, gender, race, educational level) will be recorded by the CRA from review of medical records at baseline.

#### **7.8 Medical History**

Relevant medical history, including history of current disease, and information regarding underlying diseases will be abstracted from medical records at baseline.

#### **7.9 Handling of Biospecimens Collected for Correlative Research**

Biospecimens for this study will be collected by a certified phlebotomist and stored in the Lineberger Comprehensive Cancer Center (LCCC) associated laboratory. Each sample will be assigned a unique code number and no identifiable personal health information (PHI) will be on the specimen label. Researchers with IRB-approval for access to PHI for each participant in this study will be able to link specimens to relevant medical information.

#### **Storage Time:**

- The biospecimen will be used first and foremost for research purposes outlined within the confines of this protocol. Samples will be discarded/destroyed after relevant data are collected for this study, unless consent was obtained from the patient to use her blood for other research purposes (e.g., consent form was signed by the patient). In this circumstance, biospecimens may be stored for no longer than 15 years.

### **Compliance Statement**

Biospecimen collection for this study will be conducted in full accordance with all applicable University of North Carolina (UNC) Research Policies and Procedures and all applicable Federal and state laws and regulations including 45 CFR 46, and the Health Insurance Portability and Accountability Act (HIPAA) Privacy Rule. Any episode of noncompliance will be documented.

The investigators will perform the study in accordance with this protocol, will obtain consent and assent (unless a waiver is granted), and will report unexpected problems in accordance with The UNC IRB Policies and Procedures and all federal requirements. Collection, recording, and reporting of data will be accurate and will ensure the privacy, health, and welfare of research participants during and after the study.

#### **7.10 Assessment of Safety**

Any patient who receives at least one dose of study therapy on this protocol will be evaluable for toxicity. Each patient will be assessed at least weekly during the titration of memantine and no less frequent than every three weeks during systemic chemotherapy for the development of any toxicity according to the Time and Events table. Toxicity will be assessed according to the NCI CTCAE version 5.

#### **7.11 Assessment of Efficacy**

All participants who enroll, receive at least one dose of study medication, and complete the primary outcome measure will be analyzed.

### **8.0 ADVERSE EVENTS**

#### **8.1 Definitions**

##### **8.1.1 Adverse Event (AE)**

An adverse event (AE) is any untoward medical occurrence (e.g., an abnormal laboratory finding, symptom, or disease temporally associated with the use of a drug) in a patient or clinical investigation participant administered a pharmaceutical product and which does not necessarily have a causal relationship with this treatment. An AE can therefore be any unfavorable and unintended sign (including an abnormal laboratory finding), symptom, or disease temporally

associated with the use of a medicinal product, whether or not related to the medicinal product.

Hospitalization for elective surgery or routine clinical procedures that are not the result of an AE (e.g., surgical insertion of central line) need not be considered AEs and should not be recorded as an AE.

### **8.1.2 Suspected Adverse Reaction (SAR)**

A suspected adverse reaction (SAR) is any AE for which there is a *reasonable possibility* that the drug is the cause. *Reasonable possibility* means that there is evidence to suggest a causal relationship between the drug and the AE. A suspected adverse reaction implies a lesser degree of certainty about causality than adverse reaction, which means any adverse event caused by a drug.

Causality assessment to a study drug is a medical judgment made in consideration of the following factors: temporal relationship of the AE to study drug exposure, known mechanism of action or side effect profile of study treatment, other recent or concomitant drug exposures, normal clinical course of the disease under investigation, and any other underlying or concurrent medical conditions. Other factors to consider in considering drug as the cause of the AE:

- Single occurrence of an uncommon event known to be strongly associated with drug exposure (e.g., angioedema, hepatic injury, Stevens-Johnson Syndrome)
- One or more occurrences of an event not commonly associated with drug exposure, but otherwise uncommon in the population (e.g., tendon rupture); often more than once occurrence from one or multiple studies would be needed before the sponsor could determine that there is *reasonable possibility* that the drug caused the event.
- An aggregate analysis of specific events observed in a clinical trial that indicates the events occur more frequently in the drug treatment group than in a concurrent or historical control group

#### **Assessing Causality of Adverse Events**

The likelihood of causality of all AE's will be graded as described below. Given that potential side effects of memantine overlap with those due to chemotherapy (and many other medications), we will consider not only the presence/absence of the AE, but also worsening in the severity or frequency of the AE in assessing causality.

Unrelated: Adverse event and/or its severity or frequency are clearly due to extraneous causes (e.g., underlying disease, environment)

Unlikely (must have 2): Adverse event and/or its severity or frequency:

1. does not have temporal relationship to intervention
2. could not readily have been produced by the participant's clinical state

3. could have been due to environmental or other interventions
4. does not follow a known pattern of response to intervention
5. does not reappear or worsen with reintroduction of intervention

Possible (must have 2): Adverse event and/or its severity or frequency:

1. has a reasonable temporal relationship to intervention
2. could not readily have been produced by the participant's clinical state
3. could not have been due to environmental or other interventions
4. follows a known pattern of response to intervention

Probable (must have 3): Adverse Event and/or its severity or frequency:

1. has a reasonable temporal relationship to intervention
2. could not readily have been produced by the participant's clinical state or have been due to environmental or other interventions
3. follows a known pattern of response to intervention
4. disappears or decreases with reduction in dose or cessation of intervention

Definite (must have all 4): Adverse Event and/or its severity or frequency:

1. has a reasonable temporal relationship to intervention
2. could not readily have been produced by the participant's clinical state or have been due to environmental or other interventions
3. follows a known pattern of response to intervention
4. disappears or decreases with reduction in dose or cessation of intervention

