### 5.3 Toxicities and Dosing Delays

Any patient who receives treatment on this protocol will be evaluated by the CRA, PI, or Co-Is for toxicity. Patients will be assessed at least weekly during the titration of memantine and no less frequent than every three weeks during systemic chemotherapy. For patients receiving anti-HER2 directed therapy in addition to chemotherapy, toxicity will only be assessed during the chemotherapy segment of the regimen.

Toxicity will be assessed according to the NCI Common Toxicity Criteria for Adverse Events (CTCAE), version 5.0.

In assessing adverse events (AEs) and attribution during the course of this study, we will consider those AEs commonly associated with memantine, the specific chemotherapy administered, and chemotherapy-associated medications received.

Though all patient-reported symptoms will be recorded and examined for their association with memantine, the following most common side effects of memantine will be explicitly solicited from participants by the study team: headache, dizziness, confusion, constipation, diarrhea, and fatigue. See section 6.1.7 for additional information on memantine warnings and precautions. Differentiation between memantine-associated toxicities and toxicities attributable to alternative agents will be guided by Assessing of Causality of Adverse Events outlined in 8.1.2. The treating provider will be notified of any possible, probable, or definite AEs and involved in decisions to continue, dose reduce, or stop memantine. At any time, the participant may decide to dose reduce or discontinue memantine.

If a participant experiences a grade 1 toxicity with a probable or definite attribution to memantine, the participant will remain on the same dose and symptoms will be monitored daily until the side effect is resolved.

If a participant experiences a grade 2 toxicity with a probable or definite attribution to memantine, the dose will be reduced to 5 mg PO BID (or the last tolerated dose if less) and symptoms will be monitored daily until the side effect is resolved. If no improvement, memantine will be discontinued.

If a participant experiences a grade 3 toxicity with a probable or definite attribution to memantine, the participant will discontinue memantine.

If a participant experiences toxicity with a possible attribution to memantine, the participant will remain on the same dose of memantine and symptoms will be monitored weekly until the side effect is resolved.

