If a participant experiences toxicity with an unlikely or unrelated attribution to memantine, the participant will remain on the same dose and side effects will be monitored according to the scheduled outlined in the protocol (i.e., weekly during titration or no less than every 3 weeks during maintenance).

Regardless of grade or relationship with memantine, if one of the memantine side effects listed below is the reason for dose reduction of chemotherapy, the participant will reduce memantine to 5 mg PO BID (or the last tolerated dose if less) and symptoms will be monitored daily until the side effect is resolved. If no improvement, memantine will be discontinued.

- Headache
- Dizziness
- Confusion
- Constipation
- Diarrhea
- Fatigue

Regardless of whether the participant experiences any AEs, if creatinine clearance falls below 30 mL/min, the dose will also be decreased to 5 mg PO BID. If creatinine clearance falls below 5 mL/min, the study medication will be stopped.

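### In 8.1.2 the second criterion for Unlikely is reversed, so evidence for memantine counts toward the lower causality grade

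*Combined protocol and SAP*

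**What the plan says.** **Grading (8.1.2, Assessing Causality of Adverse Events).** Unlikely needs two of five items ("Unlikely (must have 2): Adverse event and/or its severity or frequency"), Possible two of four, Probable three of four, and Definite all four. In paraphrase:

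| Fact | Unlikely | Possible | Probable and Definite |
|---|---|---|---|
| Timing | absent | present | present |
| Clinical state | does **not** readily explain the event | does not readily explain it | neither clinical state nor other causes explain it (one joint item) |
| Environment or other interventions | could explain it | could not explain it | covered by the joint item |
| Known pattern | absent | present | present |
| Response to reduction or stopping | not listed | not listed | improves |
| Reintroduction | no recurrence or worsening | not listed | not listed |

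The words "could not readily have been produced by the" participant's clinical state stand in both Unlikely and Possible. The third Unlikely item, "could have been due to environmental or other interventions", is inverted between the two lists. The opening of 8.1.2 says "Causality assessment to a study drug is a medical judgment". No rule covers an event that meets two grades.

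**Use of the grade (5.3).** Attribution is to be guided by these lists. "The treating provider will be notified of any possible, probable, or definite AEs". The rule for Possible reads "toxicity with a possible attribution to memantine, the participant will remain on the same dose of memantine and symptoms will be monitored weekly". For Unlikely or unrelated events the dose also stays the same, with checks "weekly during titration or no less than every 3 weeks during maintenance". With a probable or definite attribution, grade 2 toxicity brings a dose reduction and grade 3 a stop.

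**Duration.** Sections 5.2 and 5.5 continue memantine to 4 weeks (range 2 to 12) after the last chemotherapy dose, and 7.3 to the post-chemotherapy assessment. Sections 5.3 and 7.10 tie the 3-weekly checks to systemic chemotherapy. The 7.1 table marks the AE form and adherence only under the chemotherapy column. For anti-HER2 patients, 5.3 and 7.3 say that "toxicity will only be assessed during the chemotherapy segment of the regimen". Section 6.1.4 ends dosing with chemotherapy.

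**The concern.** A single observation cannot be evidence both for and against the drug. The other four Unlikely items all argue against memantine; item 2 argues for it. Because item 3 is inverted between the two lists and item 2 is not, this looks like a slip rather than an intention.

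The lists are operative text. Take an event with the right timing and a known memantine pattern, which clinical state does not explain but chemotherapy might. This is the overlap that 8.1.2 itself warns about. Three of its four facts favour memantine, yet staff who follow the list correctly may grade it Unlikely on items 2 and 3. The treating provider then need not be told and, after titration, the next check may be up to 21 days away instead of 7. The trial has one arm, so no concurrent control group is available to correct event-level attribution.

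**Working it through.** The plan states no figure for this point. The check enumerates the criteria.

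**Inputs (8.1.2).** Score each fact 1 if it favours memantine and 0 if not: T timing, C not explained by clinical state, E not due to environment or other interventions, P known pattern. That gives 2^4 = 16 patterns. The reintroduction item is left out at this step because 5.3 has no reintroduction step.

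- Possible = T + C + E + P, needs at least 2.
- Unlikely as written = (1 − T) + C + (1 − E) + (1 − P), needs at least 2.
- Unlikely corrected = (1 − T) + (1 − C) + (1 − E) + (1 − P) = 4 − Possible.

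Put S = T + E + P. Then Possible = S + C, and Unlikely as written = 3 − S + C.

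**As written, both grades met.** If C = 1, this needs S = 1 or S = 2, which is 3 + 3 = 6 patterns. If C = 0, Possible needs S of 2 or more and Unlikely needs S of 1 or less, so there are none. Total: 6 of 16. The 3 patterns with C = 1 and S = 2 have three of four facts for memantine. In one of them timing is absent, so Unlikely is defensible there; in the other 2 it is not.

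**Corrected, both grades met.** This needs Possible = 2 exactly: again 6 of 16, all two against two. No pattern with three facts for memantine can be Unlikely.

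**What changes.** The total does not move, but the membership does. The 3 three-to-one patterns leave. The 3 patterns with C = 0 and S = 2 enter: as written their Unlikely score is 3 − 2 + 0 = 1, so the reversal denies Unlikely to 3 two-two ties.

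**Adding dechallenge.** Let D = 1 if the event improves on reduction or stopping, giving 32 patterns. Probable = T + (C × E) + P + D, needs at least 3; its joint item is read as requiring both C and E.

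- As written: with D = 0, Probable needs T = C = E = P = 1, where Unlikely = 3 − 3 + 1 = 1. With D = 1 and C = 1, Probable needs S of 2 or more and Unlikely needs S of 2 or less, so S = 2 gives 3 patterns. With D = 1 and C = 0, Probable needs T = P = 1, where Unlikely is at most 1. Total: 3 of 32.
- Corrected: the C = 1 cases drop out. With C = 0, T = P = 1 and D = 1, Unlikely = 4 − (2 + E), which reaches 2 only if E = 0. Total: 1 of 32.

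With reintroduction added as well (64 patterns), Unlikely with Probable falls from 9 to 6, and Unlikely with Definite from 1 to 0.

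**When the check interval differs.** Both grades are checked weekly during the 3-week titration. Section 5.1 puts the last chemotherapy dose at week 9 for TC and, assuming weekly taxol from week 8, at week 19 for AC-T. With a 4-week tail, memantine time runs from 9 − 1 + 4 = 12 weeks (TC, start 1 week after) to 19 + 4 + 4 = 27 weeks (AC-T, start 4 weeks before). The post-titration share is 9/12 = 75% to 24/27 = 89%.

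**Secondary.** The 4-week tail itself is 4/27 = 15% to 4/12 = 33% of memantine time over the same cases.

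**The case against.** The strongest reply is that the lists guide a medical judgment, so a competent assessor would not grade a three-to-one event Unlikely. That stands as a limit: the text permits the lower grade and does not force it. It does not excuse a criterion that points the wrong way.

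A reader might infer that item 2 is why events can meet two grades. The counts do not support this: overlap is 6 of 16 with or without the slip, and the thresholds cause it. Nor is the error one-directional, since in 3 two-two patterns it keeps the event at Possible.

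A reader might also infer that memantine toxicity will go unrecorded or that the safety endpoint is compromised. The documents do not support that either. All symptoms are recorded (5.3), the safety endpoint is the frequency of reported AEs whatever their attribution (3.2.5), and all AEs are tabulated (9.3). If one of six listed side effects is the reason for a chemotherapy dose reduction, 5.3 reduces memantine regardless of attribution. Between Unlikely and Possible alone, the dose rule is identical. The dose consequence arises only where Probable is also met, and all 3 such patterns among the 32 presuppose that memantine was already reduced or stopped, for example by participant choice.

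On duration, a reader might infer that nobody assesses toxicity after the last chemotherapy dose. Section 7.3 calls for assessment throughout treatment, 5.3 mentions 3-weekly checks during maintenance, and 8.2 requires AE documentation, at least monthly, to 30 days after treatment stops. The anti-HER2 sentence can fairly be read as avoiding checks throughout prolonged anti-HER2 therapy. What remains is conflicting instructions, not absent capture.

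**Conclusion.** The point holds: item 2 of Unlikely is wrong as written. It opens Unlikely to 3 of 16 patterns in which three of four facts favour memantine (2 of them with the right timing), against none after correction. It also raises the Unlikely and Probable overlap to 3 of 32, against 1. Three things can change under 5.3: notice to the treating provider, the check interval after titration and, where Probable is also met, the grade 2 reduction and grade 3 stop.

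The figures count patterns, not events; the documents give no rate at which any pattern would occur. They rest on equal yes/no scoring of each fact and the joint reading of Probable item 2. The primary DMS test is unaffected. The duration conflict is minor and secondary. The wording should be corrected because it governs a safety procedure and costs little to change.

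**What to change.** **Main change, 8.1.2.** Strike the word 'not' from item 2 of Unlikely, so that a ready explanation in the participant's clinical state counts toward that grade. Add one sentence: if an event meets more than one grade, assign the highest grade met.

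Both parts are useful. Correcting the item removes the 3 three-to-one cases, and the rule settles the 6 remaining ties. The rule should not say merely that an event meeting Unlikely and Possible is Possible. Take right timing, known pattern and improvement on reduction, with both clinical state and chemotherapy as possible explanations. After correction this meets Unlikely (2), Possible (2) and Probable (3). Grading it Possible would bypass the grade 2 reduction or grade 3 stop.

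**Cost.** Amendment wording. An event moved from Unlikely to Possible brings one provider notice and, after titration, up to 2 extra checks per 3 weeks of event (3 instead of 1). An event moved to Probable brings that grade's dose rules. The documents give no event rate from which to total this.

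**Secondary alignment.** In 5.3 and 7.10, run the 3-weekly checks until memantine stops. In 5.3 and 7.3, have the anti-HER2 sentence say the same, without extending checks through later anti-HER2 therapy. In 7.1, mark the AE form and adherence at the post-chemotherapy visit, with a footnote giving the 3-weekly interval and AE documentation to 30 days after the last memantine dose. In 6.1.4, use the end of dosing given in 5.2.

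If these contacts are not already made under 7.3 and 8.2, the cost per participant is 0, 1 or 3 interim contacts for tails of 2, 4 or 12 weeks, plus one 30-day call. That is 1, 2 or 4 contacts each, or 56, 112 or 224 for 56 participants.
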